In addition to repeated episodes of suicidal self-directed violence, the study will obtain data on a number of secondary outcomes within the 12 month follow up period. These will go beyond the time to the first outcome event to include the total numbers of suicide attempts, interrupted attempts, hospitalizations for the prevention of suicide, emergency department visits, non-suicidal self-directed violent behaviors, and deaths from suicide, unnatural deaths, and all-causes. To support exploratory analyses on subtypes of suicide attempts, the study will obtain data on impulsive and non-impulsive attempts.

Following the total number of suicide attempts and time to the first attempt will allow comparison of our findings with other studies that used rates of attempts as an outcome. Following the impact of the study treatment on other forms of self-directed violence will allow us to explore the specificity of the observed treatment effects. The proposal to evaluate treatment effects on all unnatural deaths and on all-cause mortality follows from concerns that deaths from other causes in patients who have survived suicide attempts may represent suicide-equivalents or cases misclassified by medical examiners or coroners. However, we recognize that the observed rates of all-cause of mortality in persons who have attempted suicide are lower than reattempt rates, and, therefore, the study would not be powered to detect a treatment effect on overall mortality. Finally, exploratory analyses on impulsive versus non-impulsive attempts, defined on the basis of reports of the absence or presence of premeditation on the Suicide Intent Scale, may provide further insights into whether any observed effects of lithium could be related to a decrease in impulsive behaviors.

Covariates

Measures of potential effect modifiers will include traits of impulsivity and aggression. Measures of potential mediators will include symptoms of the patients' affective disorders (including suicidal ideation).

VII. BIOSTATISTICAL CONSIDERATIONS

Overview

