The primary hypothesis is that lithium is superior to placebo for the prevention of episodes of suicidal self-directed violence, including suicide attempts, interrupted attempts, hospitalizations to prevent suicide, and deaths from suicide over the ensuing year. The primary outcome measure is time from randomization for treatment allocation to the first episode. The results for event-free survival will be analyzed by means of a two-sided log-rank test. The study will have one interim analysis and one final analysis.

The duration of the study will be 4.5 years total, which allows for 3 years of recruitment, 1 year of follow-up for all enrollees, and time for start-up and closeout as indicated. A total of 1,862 patients will be enrolled and randomized to receive either lithium or placebo, both in addition to

enhanced usual care. We expect to enroll an average of 65 patients per site at 29 VA medical centers. All subjects will be followed for 12 months after randomization. Section IX describes site identification and recruitment plans.

Estimated Incidence of Primary Endpoint

We posit a 1-year event rate of 15% in the placebo group for the primary outcome based on data from the literature on lithium and SPAN data.

Lauterbach et al. (2008) reported a 12% 1-year reattempt rate in the placebo group in a cohort primarily of women, slightly younger than the VA cohort, and predominantly with major depressive disorder. This rate is slightly lower than that projected for the current study possibly because hospitalizations to prevent suicide were not included. Oquendo et al. (2011) evaluated suicide attempts and suicide events separately. Reattempt rates at 1 year were approximately 12% and 18% in the lithium and valproate groups respectively. In spite of their small samples and a more rigid definition of the endpoint, these two trials provided point estimates of outcome event rates between 12% and 18%.

To obtain a more precise estimate of the event rate in the Veteran population, we used VA SPAN data from second half of FY 2010 through the first half of FY 2012 (24 months), to characterize the target Veteran population potentially eligible for the proposed study. Detailed analysis of this cohort is presented in Section IX and selected characteristics of this target population are included and compared to the participant profiles of prior studies in Table 2.

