We considered earlier times for interim analyses, but rejected this idea because we would have only modest power to detect very large effects with even smaller sample sizes. Of note, the effects reported by Cipriani and Guzzetta (Table 2) are similar or greater than the effects to be tested in the interim analysis. We will confer with the Data Monitoring Committee members and the program leadership for potential stopping guidelines based on efficacy findings from the interim analysis.

Sample Size and Statistical Power Considerations for the Primary Hypotheses

The results for the primary outcome measure will be analyzed by a two-sided log-rank test to detect either a hazards ratio that exceeds $1/0.61 = 1.64$ or is less than 0.61. The test will have a two-sided 5% type I error overall. The test has 90% power to detect a hazard ratio of 1.64 or larger or 0.61 or less with a total of 1,862 patients, 931 per study arm which reduces to 1490 evaluable patients. This allows for 40% of subjects lost to follow-up resulting in a 20% complete data loss while on study before a repeat suicide event is observed.

Tables 3a, b, and c below consider three scenarios for possible shift in statistical power, specifically (1) in the event that an intervention effect different from the projected 37% reduction is observed (Table 3a), (2) in the event that the sample size for the study falls either above or below the targeted 1490 evaluable subject mark (Table 3b), and (3) in the event that the event rate is below the expected 15% in the placebo group. This study will have greater than 80% statistical power at 5% overall error if the observed effect is as low as 33% reduction, if the final evaluable sample is as low as 1200 subjects, or if we observe an event rate as low as 12% in the placebo group.

Secondary Data Analysis Plan

Our secondary analyses are intended:

- (a) To explore the effectiveness of lithium augmentation of enhanced suicide prevention management in preventing separately:
 - 1. all-cause mortality
 - 2. impulsive suicide reattempts
 - 3. non-impulsive suicide reattempts
 - 4. self-directed violence
- (b) To explore heterogeneity of response to treatment in subgroups including:
 - 1. categories of age, race/ethnicity, and gender
 - 2. diagnosis of depression vs. bipolar disorder
 - 3. impulsive index attempt vs. non-impulsive index attempt
 - 4. substance use vs. absence of substance use
 - 5. individuals with and without trait impulsivity

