 - 6. individuals with and without trait aggression
 - 7. subjects who have vs. have not received evidence based psychotherapies
- (c) To explore the effect of lithium augmentation of enhanced suicide prevention management on total occurrence of all event types combined and individual event type as follows:
 - 1. all suicide attempts
 - 2. all suicide attempts plus interrupted attempts
 - 3. all hospitalizations for the prevention of suicide
 - 4. all self-directed violence
 - 5. all emergency department visits
- (d) To explore longitudinally the effect of lithium augmentation of enhanced suicide prevention management on symptoms of bipolar disorder and depression and suicidal ideation
- (e) To explore mediators of the effect of lithium augmentation on prevention of episodes of suicidal self-directed violence, specifically improved control of symptoms and lithium plasma levels

Secondary objective (a) will use a time to event, survival analysis to determine whether there is a treatment difference in event rates for each of the defined endpoints. The null hypothesis for each endpoint is that the two treatment groups do not differ in their hazard rates. The alternative hypothesis is that the intervention group on lithium has a lower hazard rate than the placebo group. The log-rank test and Cox proportional hazards models will be used.

For secondary objective (b), the null hypothesis for each of the factors is that treatment effect does not differ over levels of the factor. The alternative hypothesis is that there is differential treatment effect over levels of the factor. Effect modification will be tested through the use of interaction terms in the Cox proportional hazards regression model with main effects of treatment and factor and an interaction of the two. A forest plot will be used to display the results.

Secondary objective (c) will be evaluated using Poisson regression to model for grand total numbers of events and for total number of each event type controlling for follow up time. The null hypothesis for this objective will be that total event rates do not differ by treatment assignment. The alternative hypothesis is that there is a difference in total event rates across treatment groups.

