5.2. Secondary Endpoints

There are multiple secondary endpoints being considered for the study where endpoint events for secondary objectives #1, 2, and 5 will be assessed as time to event outcomes, endpoint events for secondary objective # 3 will be assessed as count data, and endpoint events for Secondary Objective #4 will be evaluated as a binary outcome.

For Secondary Objective #1, Time from randomization to death from any cause will be analyzed. Additionally, self-directed violence as described in section 4.2 will be classified further as either impulsive or non-impulsive attempt based on Beck Suicide Intent Scale, (Question#15 on CRF-Form S8), and will be analyzed separately. Lastly, non-suicidal self-directed violence behavior defined as the primary endpoint without the death from suicide will be considered as a separate outcome.

For Secondary Objective #2 which evaluates efficacy in different subgroups, the primary endpoint as described in section 4.2 will be analyzed.

The endpoint for Secondary Objective #3 considers all components of self-directed violence as described in section 4.2. Therefore, a combined total of all episodes of all components of the primary outcome will be an endpoint, and total counts of each component, in addition to all emergency department visits will be separate endpoints.

For Secondary Objective #4, dependent variables being considered longitudinally include (1) presence or absence of symptoms, and (2) presence or absence of suicidal ideation. Presence or absence of symptoms will be derived by the Internal State Scale (CRF-Form B8), and presence or absence of suicidal ideation will be derived from the Columbia Follow Up Questionnaire (CRF-Form B6).

Lastly, for Secondary Objective #5, the endpoint event will be the same as the primary endpoint described in section 4.2.

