8.3.5. Section D: Safety Assessment (CLOSED SESSION ONLY)

Table D1. Rates of Non-Serious Related Adverse Events (NAEs), by Site and Treatment
Table D2. Rates of Serious Adverse Events (SAEs), by Site and Treatment
Table D3. **Reported in OPEN SESSION only**
Table D4. Summary of Serious Adverse Events (Form B15), by Treatment
Table D5. Related Non-Serious Adverse Events by System Organ Class, by Treatment
Table D6. Serious Adverse Events by System Organ Class, by Treatment
Table D7. Deaths Reported, by Treatment

9. Analytic Tables not included in the Data Monitoring Committee Reports

Following analytic tables will be generated annually and made available to the study team, Upon request of the DMC at the initial meeting these tables will not be included in the DMC report.

Table X1. Military Service

Table X2. Medical and Psychiatric History

Table X3. MINI Module Assessment

Table X4. Baseline Physical Assessments

Table X5. Baseline Laboratory Results

Table X6. Baseline Psychiatric Measures

Table X7. Baseline Substance Use (SCID-SUD)

Table X8. Concomitant Medications

10. Sample Size and Power

CSP590 is targeted to enroll a total of 1862 subjects, and approximately 40% of the enrolled sample is expected to terminate early (i.e., 20% complete data loss), thereby resulting in an analytic sample of 1490 evaluable subjects. With the evaluable study sample equally allocated to the 2 treatment arms, the study is powered to detect at least a 37% reduction in the one year outcome event rate.

Expected event rates used in sample size estimation to achieve 90% statistical power for hypothesis testing were 15% re-attempt rate in the placebo group and 9.45% re-attempt rate in the lithium group. Justification for selecting these rates to estimate sample size and power are provided in the protocol.

The results for the primary outcome measure will be analyzed by a two-sided log-rank test to detect either a hazards ratio that exceeds $1/0.61=1.64$ or is less than 0.61, i.e., the test has 90% power to detect a hazard ratio of 1.64 or larger or 0.61 or less.

These estimations are adjusted for an O'Brien-Fleming stopping rule with one interim and one final test of hypothesis, and allow for an overall two-sided type I error of 5% for the hypothesis being tested. Hence, the interim primary hypothesis will be tested at $p=0.002$ level (allowing for 0.2% Type I error), and the final primary hypothesis will be tested at $p=0.048$ level (allowing for 4.8% Type I error).

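### The plan asks whether lithium's effect relates to impulsive behaviour but never estimates the difference between its effects on impulsive and non-impulsive attempts

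*Protocol*

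**What the plan says.** Protocol Section VI (Other Outcomes) gives the purpose. Exploratory analyses of impulsive versus non-impulsive attempts "may provide further insights into whether any observed effects of lithium could be related to a decrease in impulsive behaviors". In the same place, tracking other forms of self-directed violence "will allow us to explore the specificity of the observed treatment effects".

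The analysis is set out in three places:

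- Protocol Section VII, secondary objective (a), lists impulsive and non-impulsive reattempts as separate endpoints. It uses survival analysis to "determine whether there is a treatment difference in event rates for each of the defined endpoints", by log-rank test and Cox model. The null hypothesis for each endpoint is equal hazards in the two arms.
- SAP 5.2 classifies events as impulsive or not from one item of the Suicide Intent Scale, "and will be analyzed separately".
- SAP 5.3 repeats the per-endpoint null and the same two methods.

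Other parts of the plan touch on impulsivity. Objective (b) (SAP objective 2) fits treatment-by-factor interactions, and two of the factors are impulsive index attempt and trait impulsivity. Objective (e) (SAP objective 5) names symptom control and lithium plasma levels as mediators. Protocol Table 6 schedules the impulsiveness and aggression scales at baseline only. SAP 5.1 describes all secondary analyses as exploratory and not powered for formal testing.

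**The concern.** The question is comparative: does lithium lower the hazard of impulsive attempts more than that of non-impulsive attempts? Two separate comparisons with placebo do not answer it. A significant result for one type and a non-significant result for the other is not evidence that the effects differ. With equal effects, that pattern arises easily when each test has moderate power.

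The plan uses the right tool, an interaction term, for patient subgroups, but not for event types. The baseline interactions ask which patients benefit, not which kind of attempt falls. Change in trait impulsivity cannot be analysed, because the scales are given once. The contrast between attempt types is therefore the only planned outcome-level evidence on impulsive behaviour, and it has no estimate attached. What is at stake is how a secondary, mechanistic result is read. The primary test, its alpha and the sample size are untouched.

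**Working it through.** **Inputs from the documents.** Protocol Section VII: "We posit a 1-year event rate of 15% in the placebo group for the primary outcome"; 9.45% on lithium; 1,490 evaluable participants, 745 per arm. Overall alpha is 0.05, two-sided, and SAP section 10 puts the final primary test at 0.048. On power, the protocol states: "The test has 90% power to detect a hazard ratio of 1.64 or larger or 0.61 or less".

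**Assumptions.** The documents give neither the share of attempts that are impulsive nor the number of events that can be classified. I vary both. I take two-sided 0.05 for each secondary test, treat the two tests as independent, and set the same true hazard ratio (HR) on both types.

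**1. The plan's own figure.**

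- HR = ln(1 − 0.0945)/ln(1 − 0.15) = 0.611.
- Events = 745 × 0.15 + 745 × 0.0945 = 182.2.
- Power = Φ(√182/2 × |ln 0.61| − 1.96) = Φ(6.745 × 0.4943 − 1.96) = Φ(1.374) = 91.5%, or 91.3% at 0.048.

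This agrees with the stated 182 events and 90% power (Protocol Table 3, SAP Table 2).

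**2. Two separate tests when the effects are equal.** With D events of one type, power is p = Φ(√D/2 × 0.4943 − 1.96). For D = 91, p = Φ(0.398) = 65.5%. Exactly one test is significant with probability p1(1 − p2) + p2(1 − p1), and 'impulsive only' with probability p1(1 − p2). At 91 and 91 events these are 2 × 0.655 × 0.345 = 45.2% and 22.6%.

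| Classifiable events | Impulsive share | Power, impulsive | Power, non-impulsive | Exactly one significant | Impulsive only |
|---|---|---|---|---|---|
| 182 | 50% | 65.5% | 65.5% | 45.2% | 22.6% |
| 182 | 40% | 55.9% | 73.3% | 47.2% | 14.9% |
| 182 | 30% | 44.7% | 79.7% | 53.2% | 9.1% |
| 182 | 20% | 32.0% | 84.7% | 62.5% | 4.9% |
| 182 | 70% | 79.7% | 44.7% | 53.2% | 44.1% |
| 146 | 50% | 56.0% | 56.0% | 49.3% | 24.6% |
| 121 | 50% | 48.5% | 48.5% | 50.0% | 25.0% |
| 91 | 50% | 38.5% | 38.5% | 47.3% | 23.7% |
| 60 | 50% | 27.2% | 27.2% | 39.6% | 19.8% |

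A participant-level simulation with competing event types (745 per arm, 182 events on average, 5,000 trials per share) gave 47%, 47%, 54% and 64% for exactly one significant at shares of 50%, 40%, 30% and 20%. At an even split the figure was 49.5% among trials whose primary result was significant.

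**3. Dependence on the true effect.** At 91 and 91 events, exactly one test is significant in 30% of trials at HR 0.80, 45% at 0.61 and 16% at 0.50. With no effect it is 9.5% if significance in either direction counts, and about 5% in simulation if only results favouring lithium count.

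**4. Direct comparison.** The standard error of the log ratio of the two hazard ratios at 91 and 91 events is √(4/91 + 4/91) = 0.2965. In the same simulations the 5% test of that ratio rejected in 5.0%, 4.3%, 4.8% and 4.9% of trials with equal effects. Its power is Φ(0.4943/0.2965 − 1.96) = 38% for a true ratio of 0.61, and Φ(0.6931/0.2965 − 1.96) = 65% for 0.50. The 95% interval runs from the estimate divided by 1.79 to the estimate times 1.79, since exp(1.96 × 0.2965) = 1.79.

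**The case against.** A reader might infer that the plan will judge specificity from two discordant tests, and so would declare a false specific effect in about half of trials. The documents do not support that:

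- The protocol speaks only of possible further insights, SAP 5.1 calls the work exploratory, and no passage says how discordant results will be read. The error rate belongs to an inference a reader might make, not to a rule in the plan.
- The figure near one half needs the design effect on both types and counts both directions. A false 'non-impulsive only' pattern would not point to impulsivity as the route of action. 'Impulsive only' is about 23% at an even split, and exceeds that clearly only if impulsive attempts are the majority.
- The 182 events include hospitalizations to prevent suicide, while the protocol ties the Suicide Intent Scale to reported attempts. Fewer events may be classifiable.
- Cox models are planned for each type as in the primary analysis, so two hazard ratios with intervals should be available, not only two p-values.
- Interactions with impulsive index attempt and trait impulsivity are pre-specified and are legitimate evidence about impulsivity.
- SAP section 11 does not list secondary results in the minimum final report, and the direct test has low power.

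All of this limits the size and severity of the point. It does not supply the missing quantity. Two intervals side by side do not give the interval for their ratio, baseline factors do not describe the type of outcome, and an exploratory label does not replace the comparison that the stated purpose needs.

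**Conclusion.** The gap is real and minor. The plan poses a question about a difference in effects between attempt types and estimates each effect without the difference.

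If one significant and one non-significant result were read as specificity, and lithium had HR 0.61 on both types, the reading would be wrong in about 45% of trials at 91 and 91 events, and in roughly 40% to 62% over the event counts and splits tried. 'Impulsive only' would occur in about 23% at an even split and in 5% to 15% at impulsive shares of 20% to 40% with 182 events. Weaker, stronger or absent effects give lower figures at 91 and 91 events: about 30% at HR 0.80, 16% at HR 0.50, and 5% to 10% with no effect. A direct test errs in about 5%.

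These figures rest on assumed impulsive shares and event counts, a 0.05 level per test and near-independent tests. Only an exploratory secondary conclusion is affected.

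**What to change.** In SAP 5.3, Objective 1:

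- Add one joint Cox model for impulsive and non-impulsive attempts, with one record per participant per attempt type, baseline hazards stratified by type, and a robust variance clustered on participant.
- State whether a participant remains at risk for the second type after an event of the first.
- Report the lithium hazard ratio for each type, their ratio with a 95% confidence interval, and the treatment-by-type test.
- State that a differential effect on attempt type will not be inferred from one significant and one non-significant result.
- Keep the planned interactions with impulsive index attempt and trait impulsivity; they answer a different question.

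The cost is a few lines of SAP text and SAS code, with no new data. The drawback is low power (about 38% for a ratio of 0.61 at 91 and 91 events), so the interval is the main output and will often be inconclusive.

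Do not extend the model to suicidal versus non-suicidal self-directed violence yet. SAP 5.2 defines the non-suicidal endpoint as the primary endpoint with suicide deaths removed, so as written it consists of suicidal events. Protocol Section VI treats non-suicidal self-directed violence as a separate class. The two must be reconciled before any such comparison can speak to specificity.

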Both stratification and blocking will be utilized to control for potential imbalances in randomization. The randomization scheme will be stratified by participating site in addition to diagnosis (bipolar vs. depression) and history of prior attempts other than the index attempt (none vs. 1+ attempt). Stratification by site is necessary because of possible regional differences in clinical practices. Participants will be randomized to either lithium or placebo within permuted random blocks of 4 so that the treatment arms are balanced after every 4th randomization within the 4 strata at each site: bipolar with prior attempt, bipolar without prior attempt, depression with prior attempt, and depression without prior attempt. Breaking the blind at the end of each participant's time in the study is not expected to provide information about the treatment assignment of participants remaining in the study as block randomization is within multiple strata. Regardless, an extra treatment assignment will be inserted to each stratum of four to disrupt the blocks and make block size harder to discern.

A web-based randomization program validated by the MAVERIC CSPCC will be provided to study sites. At subject enrollment, Site Coordinators will enter the patient ID number, study site, and eligibility information into the randomization program to confirm that all eligibility criteria are met. If met, the program will select the first unused entry from the pre-specified list of random treatment assignments for the particular site. The lists will be stored on a secure server at MAVERIC CSPCC. In case the electronic system is down, the identical process can be followed manually and the randomization scheme telephoned or faxed to the site.

This CSP clinical trial is a double-blinded study in which neither the patient nor the site investigator knows to which of the two study arms the patient has been assigned. Emergency drug code envelopes will be prepared by the CSPCRPCC and shipped with the study drugs to the Pharmacy Service of the participating medical center prior to the study starting. Each envelope is numbered with a unique patient randomization number and contains the treatment assignment for

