On the basis of studies that examined associations between suicide rates and lithium concentrations in drinking water, it has been suggested that lithium may have a preventive effect even at very low plasma levels (Helbich et al., 2012; Kabacs et al., 2011; Kapusta et al., 2011; Ohgami et al., 2009; Schrauzer & Shrestha, 1990). Based on these reports and absence of data

for what constitutes a lower limit for effective plasma levels, dose (and plasma-level) reductions will be allowed for patients who are unable to tolerate 0.6-0.8 mEq/L. The lowest allowable dose of lithium for continued treatment will be 300 mg/day. All patients able to tolerate that dose will be maintained at the highest tolerable plasma level not to exceed 0.6-0.8 mEq/L.

Blinding

This is a double blind placebo-controlled study in which the participant, treating clinicians, and all study personnel, including the Central Psychiatrist/Safety Officer, are blinded to treatment assignment.

All investigators and Outcomes Adjudication Committee members will only see blinded interim reports. Members of the DMC will receive unblinded reports in that they will view study results by treatment group (e.g. A versus B) and these designations will be randomly assigned within a report. The placebo will be produced by the CSPCRPCC and be nearly identical in appearance to the active agent and have similar taste and odor.

Breaking the blind, to the patient's mental health provider, at the end of a participant's time in the study should not compromise the blind for the personnel at the study site nor influence outcome assessments of participants remaining in the study. All ratings and assessments will be completed before the blind is broken. To ensure that the breaking the blind on those who complete the study does not reveal information about the assignment of the last subjects, block randomization is within multiple strata and an extra treatment assignment will be inserted to each stratum of four to disrupt the blocks and mask block sizes, as described in Section VII.

Titrating study medication

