At the conclusion of the 1-year study treatment, participants will be referred to their treating mental health provider for continued management. There are data to suggest that suicidality and mood disturbances may be increased after stopping lithium. To insure continuity, the appointment with the subject's providers will be scheduled well before completion of the study. The Research Team will maintain responsibility for the subject until they have been seen by their treating clinician in a face-to-face encounter; the goal will be to provide warm-hand-offs through encounters that include the Research Team, the clinical provider, and the patient whenever possible. The research team will ensure that each study participant has a prescribing mental health provider assigned to him/her prior to study Month 10.

At the End of Study visit, the participant and the treating mental health provider will be informed of the treatment assignment. They will be reminded about the possible risks associated with rapid withdrawal of lithium and the need for a slow taper if lithium is to be discontinued. Patients will be asked to return for a 30-day follow-up study visit.

Patients who withdraw consent

Participants withdrawing consent will be asked to participate in a final study assessment. The blind will be broken at the time of this assessment and no further data will be collected. The Research Team will contact the participant's treating mental health provider to recommend gradual tapering of lithium as needed.

Patients who discontinue study treatment prior to 1 year

The investigator may discontinue the study medication for any reason, including adverse effects, safety concerns or protocol violations. In addition, participants may elect to discontinue study medication at any time. Discontinuation of study medication will not automatically result in withdrawal of the participant from the trial, nor unblind the study treatment. The investigators will encourage the participant to continue with study assessments but they will not be required to complete EKGs, blood draws or vital signs except for the 30 day follow-up visit (see Table 7). If a participant does not agree to continue assessments, the blind will be broken, to the participant's mental health provider, at the time they are tapered or discontinued. All ratings and assessments will be completed before the blind is broken.

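### The protocol does not say how site staff stay blind at the end-of-study hand-off, and its printed blocking scheme lets a revealed arm hint at others still in follow-up

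*Protocol*

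**What the plan says.** **Allocation.** Protocol VII (Randomization Plan) allocates in "permuted random blocks of 4 so that the treatment arms are balanced after every 4th randomization", and does so "within the 4 strata at each site". The strata are diagnosis by prior attempt. Unblinding at the end of each person's participation "is not expected to provide information about the treatment assignment of participants remaining in the study as block randomization is within multiple strata". As a further safeguard, "an extra treatment assignment will be inserted to each stratum of four to disrupt the blocks and make block size harder to discern". Protocol XIII (Blinding) repeats this device.

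**Disclosure.** Protocol XIII speaks of breaking the blind to the mental health provider and says this "should not compromise the blind for the personnel at the study site". Protocol V (rationale for the inclusion criteria) places the provider's unblinding at the hand-off, where provider and participant may choose to continue, taper or start lithium. Protocol XIV (patients who complete 1 year) has both participant and provider told at the End of Study visit, and sets as a goal "warm-hand-offs through encounters that include the Research Team, the clinical provider, and the patient whenever possible". The participant is then asked back at 30 days, a contact at which Table 6 schedules a VA record review.

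**Who holds the protocol.** Protocol XVII (Training on Study Measures) sends it to site investigators and coordinators.

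**The concern.** The blinding statement and the hand-off procedure do not fit together as written. Staff who sit in an encounter with an unblinded provider, while the future of lithium treatment is discussed, can hardly avoid learning that participant's arm. That participant's own ratings are already complete. The exposure is to block-mates who are still being assessed.

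Stratification is weak protection against this observer. It hides the block from an outsider. The site, however, enrolled these people and can know each one's diagnosis, attempt history and order of entry, and the block size and the disruption device are printed in a document the site holds.

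Site staff conduct the Columbia interviews, adjust doses and assemble the event reports. SAP 4.2 says potential endpoints come mostly from serious adverse event reports and the Columbia follow-up form, so what staff elicit and submit determines what the adjudicators see. Protocol VIII rejected open designs because knowing who was on lithium could change providers' decisions, so the plan itself treats the blind as important.

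**Working it through.** **Step 1. Size of a stratum.** Inputs: "A total of 1,862 patients will be enrolled and randomized" (Protocol VII Overview); 29 sites, 65 per site on average, 3 years of accrual and 12 months of follow-up (Protocol IV and VII).

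- Per site: 1862 / 29 = 64.2, against the stated 65 (29 × 65 = 1885). This agrees to within rounding.
- Per stratum: 64.2 / 4 = about 16 if strata are equal (assumption; 8 to 32 if not).
- Spacing: 36 / 16 = 2.25 months between entries. A block of 4 fills in about 4 × 2.25 = 9 months, and a block of 5 in about 11.25. Both are shorter than the 12-month follow-up, so block-mates are usually still under assessment when the first one finishes.

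**Step 2. Exact leak when all earlier arms in the block are known.** A plain block of 4 has 6 equally likely sequences. Adding one random assignment to a block always gives a 3:2 or 2:3 split, with 20 equally likely sequences. For each position:

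| Position | Plain 4: certain / best guess right | 4 plus 1: certain / best guess right |
|---|---|---|
| 1 | 0 / 0.500 | 0 / 0.50 |
| 2 | 0 / 0.667 | 0 / 0.60 |
| 3 | 0.333 / 0.667 | 0 / 0.60 |
| 4 | 1 / 1 | 0.10 / 0.70 |
| 5 | – | 0.40 / 0.70 |
| Mean | 33.3% / 70.8% | 10.0% / 62.0% |

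For example, position 5 is certain when the first four split 3:1 (probability 0.40) and is a coin toss when they split 2:2, so the best guess is right 0.40 + 0.60 × 0.5 = 0.70 of the time. The device cuts certainty from 33.3% to 10.0% but does not remove it.

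**Step 3. Realistic timing.** Simulation: uniform accrual over 36 months, 16 per stratum, 40% dropout (the planning figure in Protocol VII, Missing Data from Attrition) at uniform times, one extra per block, and an observer who tracks strata and order.

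| Arms known to the site | Certain | At least two-thirds predictable |
|---|---|---|
| Every completer | about 1% | about 13 to 15% |
| Half of completers | 0.2% | 4% |
| Every exit, including early ones | about 9% | 34% at end of own follow-up |

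In the first row, certainty covers about 0.4% of follow-up time, and time after first reaching two-thirds about 5%. For comparison, plain blocks of 4 would give about 8% certain (completers known) or 33% (all exits known).

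**Step 4. Ambiguity of the device.** The phrase about a stratum of four can mean each block or each of the four stratum lists. With one extra per list of 16 at an unknown position, and all earlier arms known, 17.1% of participants are predictable with probability 0.9 or more and the best guess is right 66.5% of the time. The per-block figures on the same basis are 10.0% and 62.0%.

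**Step 5. Would varying block sizes alone help?** If the scheme is known and completers' arms are revealed, randomly mixed blocks of 4 and 6 give 0.6% certain and 12% at least two-thirds predictable, against about 1% and 15% for the current device. That is little gain.

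**The case against.** A reader might infer that sites learn each completer's arm. The documents do not say that. Those told are the participant and the treating provider, the Research Team is not named among them, and its attendance is a goal. What is documented is a gap: nothing says how the team stays blind in a shared encounter.

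A reader might also take the scheme to be bare blocks of 4. It is not. The protocol saw this risk and added a safeguard, and the plain-block figures are only a comparator.

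The all-exits scenario is an upper bound. Under Protocol XIV, stopping study medication does not by itself unblind. If the participant also declines further assessments, the blind is broken to the provider. Deaths are not unblinded. Only for withdrawal of consent is the recipient left unstated.

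The effect on outcomes is buffered. Two independent reviewers, blinded to assignment, classify events from medical records and the patient's own account (Protocol VI). The inference is mostly probabilistic, comes late in follow-up, and needs someone at the site to keep track. The conflict between balance after every fourth entry and an inserted extra is a wording matter, since the extra is openly introduced as a modification.

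All of this stands and limits the size of the problem. It does not close the gap, because adjudicators see what sites identify and assemble.

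**Conclusion.** The point holds as a low-priority improvement. The sections on the hand-off (Protocol V and XIV) and on blinding (Protocol XIII) are not reconciled, and the reassurance in Protocol VII is weaker than it reads, because strata do not hide blocks from the site that fills them. The result is a residual risk of partial unblinding of the staff who interview participants and assemble event reports.

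The size is modest: about 1% certain and 13 to 15% at least two-thirds predictable if every completer's arm reaches the site, and about 9% certain at the upper bound. These figures assume one extra per block, equal strata of about 16, 40% uniform dropout and an observer who tracks order. They shrink if fewer arms leak, and grow if the extra is inserted only once per stratum list. They do not show that outcomes would be biased, and the documents do not allow that to be estimated.

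**What to change.** 1. Have the coordinating center or pharmacy send the assignment directly to the treating provider. Disclose it to provider and participant without the Research Team members who assess other participants present. State who receives it when consent is withdrawn.
2. Reconcile Protocol V, XIII and XIV so that all three name the same recipients and occasion.
3. Remove the block size and the disruption device from site-held documents, and keep them only at the coordinating center. Undisclosed, varying block sizes are optional. The protection comes from non-disclosure, since known blocks of 4 and 6 do little better than the present device.
4. In the coordinating center's randomization specification, state whether the extra is per block or per stratum list, and reconcile it with the statement of balance after every fourth entry.

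The cost is minor document changes, a slightly less integrated hand-off and, if block sizes vary, a slightly larger possible imbalance within a site stratum. Sample size and the primary analysis are unaffected.
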